7. STUDY DEFINITIONS

7.1. Disposition

Study Completion: Subjects who complete study at the End of Study (EOS) visit are considered as achieving study completion.

Treatment Completion: Subjects who complete the End of Treatment (D6/EOT) visit on *Day 6* are considered as achieving treatment completion.

7.2. Reference Start Date and Study Day

Reference Start Date (Day 1) is defined as the date of first dosing of study drug (BA or FCDP).

Study Day will be calculated from the reference start date and will be used to show start/stop day of assessments and events.

Study Day will be calculated as follows:

- If the date of the event is on or after the reference date, then Study Day = (date of event - reference start date) + 1.
- If the date of the event is prior to the reference date, then Study Day = (date of event - reference start date).

The Study Day will be used to show start/stop day of assessments and events (including AEs, prior and concomitant medications). In the situation where the event date is partial or missing as entered in the EDC database, the date will be displayed as such in the listings. Study Day and any corresponding duration(s) will be presented based on the imputations specified in [Appendix 2](#).

7.3. Baseline

Baseline is defined as the last non-missing measurement taken on or prior to initial IMP on Day 1 (including unscheduled assessments), unless otherwise specified.

7.4. Prior and Concomitant Medications

Prior medications are medications which started and ended prior to Day 1.

Concomitant medications are medications that started after Day 1 and continued during the study, or that started before or on Day 1 and continued through Day 1 (“ongoing” at Day 1 or ended after Day 1).

8. STATISTICAL CONSIDERATIONS

8.1. Sample Size

A minimum sample size of 16 (8 subjects who receive BA [Cohort 1] and 8 subjects who receive FCDP [Cohort 2]) evaluable subjects (who complete the 6-day treatment period and the 24-hour breast milk collection in the CRU) is planned for this study. Subjects who are treated but do not complete the 24-hour breast milk collection in the CRU will be replaced with a new subject on the same treatment to ensure 8 evaluable subjects in each cohort for the PK analyses. All treated subjects will be in the FAS.

The sample size was not based on empirical or hypothesis testing criteria. The sample size was based on clinical and regulatory considerations and precedence in previous ETC-1002 studies (████████). The sample size is considered sufficient to address the primary objectives of the study.

8.1. Number of Centers

The study will be conducted in up to 2 CRUs in the United States. Additional sites may be invited to participate to ensure study timelines are met.

8.2. Coding Dictionaries

Adverse events, medical history diagnoses or signs/symptoms, and concomitant procedures are coded using Medical Dictionary for Regulatory Activities (MedDRA) version 26.0 including system organ class (SOC), high level term (HLT) and preferred term (PT).

Prior and concomitant medications are coded using WHO Drug Dictionary (WHO-DD) Global B3 version 01Mar2023.

8.3. General Principles

Descriptive statistics (n, mean, standard deviation, median, 1st quartile, 3rd quartile, minimum, and maximum) will be calculated for continuous data. Minimum and maximum will be presented with the same number of decimal places as reported/collected, 1 additional decimal place will be included for mean and median, and 2 additional decimal places will be included for standard deviation.

Categorical data will be summarized using count and percentage based on number of non-missing values. Percentages will be presented with 1 decimal place. The number of missing values will be presented as a separate category when appropriate. Counts of zero in any category will be presented without percentage.

8.4. Missing Data Handling

Unless otherwise specified, missing data will not be imputed.

8.4.1. Imputation of Missing Dates

For adverse events, and for prior and concomitant medications, if the start and/or end dates are incomplete, then the date will appear as-is (partial or missing) in the listings. When a complete

date is needed, e.g., to compute the Study Day, imputation rules specified in [Appendix 2](#) will be used unless otherwise specified. In essence, AEs of uncertain start date will be considered as having started after the first dose of study drug. Medications of uncertain start or end dates will be considered as having started before, or continued after the first dose of study drug, respectively.

8.4.2. PK and Laboratory Data Beyond the Limits of Quantification

Day 1 pre-dose concentrations below the limit of quantitation (BLQ) will be imputed as zero.

Day 6 pre-dose PK concentrations in breast milk were not collected in this study. To facilitate the determination of AUC_{24h} in breast milk, a Day 6 pre-dose concentration value is needed. Since subjects will be near steady state after 6 days of bempedoic acid dosing, the Day 6 pre-dose concentration will be imputed as the trough concentration value on Day 7 at 24 hours post-dose for individual subjects. If a concentration of BLQ is before the last quantifiable value of the subject, it will be marked with an exclusion flag and excluded from analysis. The BLQ concentrations that are at the end of the concentration curve will be imputed by half of the lower limit of quantitation (LLOQ) for the purpose of quantitative summaries.

All PK concentration of BLQ values will be presented as reported, i.e., as “BLQ<(xx.x)” in the listings.

Biomarker and safety laboratory measurements reported as “<X” or “>X” will be imputed as X for the purpose of quantitative summaries, but will be presented as reported, i.e., as “<X” or “>X” in the listings.

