#### **4.3 Dose Selection**

A dose of bempedoic acid 180 mg once per day was selected based on approved doses by the US FDA ([Nexletol](#)) and the European Medicines Agency ([Nilemdo](#)). The dose for bempedoic acid/ezetimibe FCDP (bempedoic acid 180 mg/ezetimibe 10 mg) was selected based on approved doses by the US FDA ([Nexlizet](#)) and the European Medicines Agency ([Nustendi](#)). For additional information please refer to the most recent [IB](#), the [USPIs](#) for [Nexletol](#) and [Nexlizet](#) and the [SmPCs](#) for [Nilemdo](#) and [Nustendi](#).

Subjects enrolled in the study will be dosed for 6 consecutive days in order to reach steady-state concentrations of bempedoic acid or bempedoic acid and ezetimibe in plasma. Steady-state concentrations in plasma are expected after 5 to 7 days of repeat dosing as estimates of elimination half-life of bempedoic acid and ezetimibe are each approximately 24 hours. A once daily dosing regimen for 6 days will achieve plasma concentrations that are approximately 98% of steady-state levels. Six days of repeat dosing have been selected to ensure subjects are at steady-state plasma concentrations of bempedoic acid or bempedoic acid and ezetimibe for pharmacokinetic (PK) assessments.

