#### **10.3.4.2 Treatment Day 6**

The 24-hour breast milk collection will start the morning of Day 6 and end the morning of Day 7. The following assessments/procedure will be performed prior to the initiation of the 24-hour breast milk collection:

- adverse event review;
- concomitant medication review; and
- subject will pump both breasts with an electric pump until empty prior to administration of the last dose of IMP.

Once both breasts have been completely emptied on the morning of Day 6, Cohort 1 subjects will receive the Day 6 dose of bempedoic acid and Cohort 2 subjects will receive the Day 6 dose of bempedoic acid/ezetimibe FCDP. Breast milk will be collected from each subject over the next 24 hours using an electric pump at 3, 6, 9, 12, 16, 20 and 24 hours ( $\pm 30$  minutes) after Day 6 dose administration.

At each collection time point, subjects will pump both breasts until empty, breast milk collected from each breast will be mixed together and the total volume measured and recorded. Breast milk from each time point will be stored according to procedures outlined in the Laboratory Manual and [Section 11.1](#).

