## **11. PHARMACOKINETIC ASSESSMENTS**

### **11.1 Breast Milk Sample Collection and Processing**

Breast milk will be collected using an electric pump. Breast milk samples will be collected within 1 hour before IMP dosing (predose) on Day 1 and on Day 6 at 3, 6, 9, 12, 16, 20 and 24 hours ( $\pm$ 30 minutes) after IMP dosing on Day 6. Subjects will be instructed to completely empty both breasts at each sampling time point. At each sampling time point, milk collected from each breast will be mixed together and the total volume will be measured and recorded. From each combined sample 2 aliquots (approximately 5 mL) of breast milk will be transferred to appropriately labeled tubes and stored at or below -70° Celsius within 30 minutes of collection. Breast milk samples from each time point will be stored according to procedures outlined in the Laboratory Manual.

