### 14.2 Determination of Sample Size

A minimum sample size of 16 (8 subjects who receive bempedoic acid [Cohort 1] and 8 subjects who receive bempedoic acid/ezetimibe FCDP [Cohort 2]) evaluable subjects (who complete the 6-day treatment period and the 24-hour breast milk collection in the CRU) is planned for this study. Subjects who are randomized but do not complete the 24-hour breast milk collection in the CRU will be replaced with a new subject on the same treatment to ensure 8 evaluable subjects in each cohort for the final analyses.

The sample size was not based on empirical or hypothesis testing criteria. The sample size was based on clinical and regulatory considerations and precedence in previous ETC-1002 studies (████████). The sample size is considered sufficient to address the primary objectives of the study.

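### Milk pumped just before the Day 6 dose is not assayed, so the time-zero value behind RID is imputed and no concentration can flag a missed late home dose

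*SAP*

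**What the plan says.** Protocol 10.3.4.2 requires that, on the morning of Day 6, the "subject will pump both breasts with an electric pump until empty prior to administration of the last dose of IMP". Protocol 11.1 lists the milk PK samples as those taken "within 1 hour before IMP dosing (predose) on Day 1 and on Day 6 at 3, 6, 9, 12, 16, 20 and 24 hours" after dosing. SAP 17.1 gives the same times, so the Day 6 pre-dose milk is not on either list.

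SAP 8.4.2 says that "Day 6 pre-dose PK concentrations in breast milk were not collected in this study", that for AUC24h "a Day 6 pre-dose concentration value is needed", and that "the Day 6 pre-dose concentration will be imputed as the trough concentration value on Day 7". SAP 17.4 repeats the rule. Its stated reason is that women are near steady state after six days of bempedoic acid. AUC24h divided by 24 gives Cavg, and Cavg times 150 mL/day/kg is the numerator of RID (SAP 17.3). The other primary endpoint, daily infant dosage, sums concentration times volume over the post-dose collections and uses no time-zero value.

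The steady-state premise comes from Protocol 4.3: "estimates of elimination half-life of bempedoic acid and ezetimibe are each approximately 24 hours", and "A once daily dosing regimen for 6 days will achieve plasma concentrations that are approximately 98% of steady-state levels". No half-life is given for ESP15228 or for the two glucuronides.

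Doses on Days 2 to 5 are taken at home (Protocol 8.1). Adherence is judged from phone calls, the diary and a count of returned tablets (Protocol 9.4; SAP 16). Plasma is drawn only before the first dose and 24 h after the Day 6 dose (Protocol 11.2).

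**The concern.** An input to a primary endpoint is imputed although the milk that would supply it is pumped in the unit minutes before the dose. The imputation also builds the steady-state premise into the data. With C0 set equal to C24, the two troughs agree by construction, and neither milk nor plasma has a second on-treatment trough to compare.

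If a woman missed a late home dose and the calls, diary and tablet count did not reveal it, her Cavg and RID would be too low, which understates infant exposure. Nothing in her concentrations would point to it. With eight women per cohort, one such case is visible in the cohort mean.

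**Working it through.** **Inputs.** From the documents: half-life about 24 h, six daily doses, milk at 3, 6, 9, 12, 16, 20 and 24 h, linear-up/log-down AUC (SAP 17.4). There is no power calculation to reproduce ("The sample size was not based on empirical or hypothesis testing criteria"). Assumed, because the documents are silent: one-compartment oral model, milk proportional to plasma, absorption rate 0.3-3 per h, half-life varied from 16 to 36 h.

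**1. The plan's own figure.** Fraction of steady state after n doses = 1 - 0.5^(24n/half-life). For n = 6 and 24 h: 1 - 0.5^6 = 98.4%, which agrees with the stated 98%. Before the Day 6 dose, n = 5: 1 - 0.5^5 = 96.9%.

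**2. Direct effect of the imputation on RID.** C0 enters only the first trapezoid (0-3 h). Concentration rises over that interval in the cases below, so the linear rule applies and the AUC error is 1.5 h x (C24 - C0). Each dose contributes ka/(ka - k) x [exp(-kt) - exp(-ka t)], with k = ln 2/24 and ka = 1 per h:
- All doses taken: C0 = 0.998, C24 = 1.014, AUC24h = 33.40. Error 1.5 x 0.016 = 0.024, or 0.07%.
- Day 5 missed: C0 = 0.483, C24 = 0.756, AUC24h = 24.48. Error 1.5 x 0.273 = 0.41, or about 1.7%.

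Over all assumed absorption rates and half-lives the error is 0.01-0.21% with full dosing and 1.3-2.4% after a missed Day 5 dose. At 24 h, missing all four home doses gives about 4-5%.

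**3. Effect of the missed dose itself.** With Day 5 missed, true AUC24h changes by 24.48/33.40 - 1 = -27% (27-28% lower over the absorption rates at 24 h). One such woman among eight lowers the cohort mean by about 27/8 = 3%.

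**4. What a measured C0 would show.** Taking each dose as halving every 24 h:

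| Home dosing | C0 | C24 | C0/C24 |
|---|---|---|---|
| All taken | 0.969 | 0.984 | 0.98 |
| Day 5 missed | 0.969 - 0.5 = 0.469 | 0.984 - 0.25 = 0.734 | 0.64 |
| Day 4 missed | 0.969 - 0.25 = 0.719 | 0.984 - 0.125 = 0.859 | 0.84 |

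**5. Noise in that ratio.** Protocol 8.1 allows doses within 2 h of the usual time, and a forgotten dose up to 6 h later. Moving only the Day 5 dose changes its contribution to C0 from 0.5 to 0.5^(interval/24), and C24 = 0.5 + C0/2:
- 2 h early: 0.941/0.970 = 0.97.
- 2 h late: 0.998/0.999 = 1.00.
- 6 h late: 1.063/1.032 = 1.03.

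Pooling adds more. The 24-h sample pools 4 h of milk, while the interval before the Day 6 pumping is not fixed. Relative to the end of an interval of L hours, the average is (2^(L/24) - 1)/((L/24) ln 2): 1.060 for 4 h and 1.125 for an assumed 8 h, a shift of about 6%.

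**6. Can the ratio test half-life?** With full dosing, assumed half-lives of 24, 36 and 48 h give C0/C24 of 0.984, 0.901/0.938 = 0.96 and 0.823/0.875 = 0.94. That 4-point spread is smaller than the 6 points from permitted dose timing alone.

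**The case against.** The strongest reply is that the imputation is prespecified, made woman by woman, openly justified, and nearly harmless to RID. That stands, and it is why this is a modest improvement and not a defect in the primary analysis.

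Several stronger readings are tempting, and the documents do not support them:
- **Home dosing cannot be checked.** It is checked. Staff call daily, review a timed diary and count returned tablets (Protocol 9.4). SAP 16 classes anyone below 100% as non-compliant. A woman known not to have had six doses is to be replaced (Protocol 6.7). What is absent is a check based on concentration.
- **The Day 6 pre-dose milk is thrown away.** No passage says what happens to it. The discard footnote in Appendix 1 covers Days 1-5 and 7-13. All that can be said is that it is not a listed PK sample.
- **C0/C24 would verify steady state.** Steps 5 and 6 show that permitted timing and pooling swamp the signal of a longer half-life.
- **The missing aliquot costs about a quarter of RID.** That is the effect of a missed dose. A measured C0 would reveal the miss but would not restore RID.
- **Unknown metabolite half-lives undermine the primary endpoints.** RID and daily infant dosage are defined for bempedoic acid and ezetimibe only. The gap affects the metabolites' secondary AUC24h and Cavg.

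SAP 8.4.2 is also worded in the past tense, so the chance to collect the sample may have gone.

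**Conclusion.** The point holds as a low-cost improvement. A measured value could replace an imputed input to RID, and the plan gives up the one within-woman comparison that could flag a missed late home dose. The numerical error from the imputation is minor and leaves daily infant dosage untouched. The useful signal is a ratio near 0.64 for a missed Day 5 dose, well outside the range that permitted timing produces. The 0.84 for Day 4 is closer to the noise, and earlier misses would be hard to see.

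These sizes rest on the stated 24-h half-life, on milk tracking plasma, and on the assumed absorption rates. At assumed half-lives of 16 and 36 h the Day 5 ratio would be about 0.45 and 0.75, still separate from full dosing.

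**What to change.** Keep and assay the standard aliquots from the Day 6 pre-dose pumping, and record the volume and the time since the previous emptying so that the pooled sample can be interpreted. Add the sample to Protocol 10.3.4.2, 11.1 and Appendix 1, and to SAP 17.1. In SAP 8.4.2 and 17.4, use the measured value as C0 and fall back on C24 only when it is missing. List C0/C24 by woman as a flag for a missed Day 5 or, less clearly, Day 4 dose, and say that it is not a test of half-life or of slow accumulation.

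The cost is one more assayed milk sample per woman and small edits to the protocol, SAP and laboratory manual. No pumping, visit or blood draw is added.

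If collection is already complete, report the sensitivity of RID to C0 and state as a limitation that steady state was assumed, including for the metabolites, for which no half-life is given.

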9. DISPOSITION AND WITHDRAWALS

All subjects who were screened will be accounted for in this study. Reasons for screen failure will be summarized by pre-defined categories per the Screen Failure eCRF. For screen failures due to inclusion or exclusion criteria violation, the criteria category will be presented in a listing.

The number of subjects in each analysis set, along with study completion status, will be summarized by treatment group as well as overall. Subjects who discontinue from study treatment and/or study will be summarized by discontinuation reason.

A listing of subject disposition will be provided for all randomized subjects, including the treatment and study completion status, and discontinuation reasons, and/or reasons of being excluded from FAS, PKS.

10. PROTOCOL DEVIATIONS

The protocol deviations will be recorded and tracked in the Clinical Trial Monitoring System. All protocol deviations will be reviewed by the clinical team to identify important versus non-important deviations before the final EDC database lock. The final list of protocol deviation will be approved by the study team prior to the EDC database lock and will be used to generate the protocol deviation summary and listing.

For deviations at study entry, subject eligibility will be assessed against the inclusion and exclusion criteria of the protocol. For on-study deviations, compliance with the protocol will be determined via periodical data and monitoring report review.

All protocol deviations will be provided in a listing. Important protocol deviations will be summarized by treatment group and deviation categories for SES.

11. DEMOGRAPHIC AND OTHER BASELINE CHARACTERISTICS

Demographic data and other baseline characteristics will be summarized by treatment group for the FAS, PKS.

The following demographic and other baseline characteristics will be reported for this study:

- Age (years [yrs])
- Race
- Weight (kg)
- Height (cm)
- Body mass index (BMI) (kg/m²)
- BMI group (kg/m²) (<25, 25 ~ <30, or ≥30)

12. MEDICAL HISTORY AND POSTPARTUM HISTORY

12.1. Medical History

Medical information will be presented by Medical Dictionary for Regulatory Activities (MedDRA) SOC and PT for the SES. Medical history conditions are defined as those conditions which started prior to signing of the ICF. Medical history will be coded using MedDRA in most recent version when the study started ([Section 8.2](#)).

12.2. Postpartum History of Recent Pregnancy

The postpartum history, including gestation age at delivery and length of postpartum, will be collected at screening and summarized by cohort and for overall FAS.

13. LACTATION STAGE

The lactation stage (lactating/weaning/weaned off) and related information will be collected at Screening and T1 (Day 1) visits. Subject listing of lactation stage, including start date of lactation or weaning, duration of lactation or weaning, and date of weaned off will also be provided.

14. CURRENT FEEDING PRACTICE

Current feeding practice will be collected at Screening and T1 (Day 1) visit.

Number and percentages of subject who produced adequate breast milk, and number and percentages of subject who fed their infant with formula supplementation will be summarized by cohort and for overall on FAS.

The frequency of feeding and the volume of pumped breast milk consumed per day, and the volume of infant formula consumed per day will be summarized by cohort on FAS.

15. PRIOR AND CONCOMITANT MEDICATIONS

Prior and concomitant medications will be presented for the SES. In general, the medications will be summarized by Anatomical Therapeutic Chemical (ATC) drug class (ATC level 4, anatomical or pharmacological groups), preferred names, and by cohort.

- Prior medications are medications which started and stopped prior to the date of first dose of study drug.
- Concomitant medications are medications that started prior to and continued through the date of the first dose of study drug.

See [Appendix 2](#) for handling of partial dates for prior medications and concomitant medications. Prior and concomitant medications will be tabulated separately and reported in a subject listing.

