### **8.2 Prior and Concomitant Medications**

Any medication or vaccine (including over the counter or prescription medicines, vitamins, and/or herbal supplements) that the subject is receiving at the time of enrollment or receives during the study must be recorded in the eCRF along with:

- reason for use,
- dates of administration including start and end dates, and
- dosage information including dose and frequency.

Subjects will be permitted to take concomitant medications except those listed in [Section 8.2.1](#).

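### SAP Sections 15 and 7.4 define concomitant medication differently; if Section 15 is programmed as written, medications with a known start on or after the first dose fall outside the medication tables

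*SAP*

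**What the plan says.** SAP Section 15 sets out the medication summaries by ATC class, preferred name and cohort, and gives its own two definitions. For prior medication: "Prior medications are medications which started and stopped prior to the date of first dose of study drug". For concomitant medication: "Concomitant medications are medications that started prior to and continued through the date of the first dose of study drug". It then fixes the outputs: "Prior and concomitant medications will be tabulated separately and reported in a subject listing".

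SAP Section 7.4, among the study definitions, gives a wider rule: "Concomitant medications are medications that started after Day 1 and continued during the study, or that started before or on Day 1", where the second group must also have continued through Day 1. A parenthesis explains that condition as still ongoing at Day 1 or ended after it.

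Both sections use the same anchor, since SAP Section 7.2 states: "Reference Start Date (Day 1) is defined as the date of first dosing of study drug (BA or FCDP").

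On data collection, Protocol Section 8.2 says that any medication or vaccine the subject "is receiving at the time of enrollment or receives during the study must be recorded in the eCRF". Protocol Sections 10.3.2 to 10.3.5 repeat the concomitant medication review after the first dose, up to the Day 13 call (FU1).

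**The concern.** Two sections of one SAP give different classifications from the same start and stop dates. Section 15 neither refers to Section 7.4 nor says that it replaces it. The general rule that the SAP supersedes the protocol does not help, because the conflict lies inside the SAP.

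Section 15 is where a programmer building the tables would look. Its two classes leave a gap: each requires a start before the first dose, so a medication begun on study belongs to neither. Those new starts are what the post-dose reviews exist to find. Many would be permitted drugs, taken with the consent required by Protocol Section 8.2.2. They are not protocol deviations, so the concomitant medication output is the natural place to report them.

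At stake is whether the medication tables, and perhaps the listing, describe what the women took during the study or only what they were already taking when dosing began.

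**Working it through.** The plan gives no figure to reproduce. The check applies both definitions, as written, to the same medication dates.

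**Inputs.** Day 1 is the first-dose date (SAP 7.2). Write s for the start day and e for the stop day, both known.

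**Rules as written.**
- Section 15: prior if s and e are both before Day 1; concomitant if s is before Day 1 and the drug continued through Day 1.
- Section 7.4: prior if s and e are both before Day 1; concomitant if s is after Day 1, or if s is on or before Day 1 and the drug was ongoing at Day 1 or ended after it.

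**Example cases.**

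| Start | Stop | Section 15 | Section 7.4 |
|---|---|---|---|
| Day -10 | Day -3 | prior | prior |
| Day -10 | Day 5, or ongoing | concomitant | concomitant |
| Day -10 | Day 1 | concomitant, if through is read inclusively | unclear |
| Day 1 | Day 1 | neither | unclear |
| Day 1 | Day 4 | neither | concomitant |
| Day 3 | Day 4 | neither | concomitant |
| Day 6 | Day 7 | neither | concomitant |
| Day 9 | Day 12, or ongoing | neither | concomitant |

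**All cases within Days 1 to 13.** The number of pairs with 1 ≤ s ≤ e ≤ 13 is 13 + 12 + … + 1 = 13 × 14 / 2 = 91.
- Section 15: every pair has s ≥ 1, so neither class can apply. Concomitant: 0 of 91.
- Section 7.4: every pair qualifies except s = e = 1. Concomitant: 90 of 91.

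These count possible date patterns. They do not predict how many medications the trial will record.

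**Illustration.** Suppose one woman in a cohort of 8 starts a permitted drug on Day 3 and no other woman takes it. Section 7.4 gives 1/8 = 12.5% for that drug; Section 15 gives 0/8.

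**Incomplete dates.** SAP Section 8.4.1 treats a medication with an uncertain start as begun before the first dose, and Appendix 2 sets a missing start day to the first of the month. A drug that really began on Day 3 but lacks its day may thus be moved to before dosing and counted under Section 15. The same drug with its exact date recorded is left out.

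**The case against.** The strongest reply is that nothing need be lost. Section 7.4 sits under the study definitions and plainly includes on-study starts; a programmer who follows it produces a sensible table. That stands. A reader might infer from Section 15 that every medication begun during treatment or washout will certainly disappear, but the documents do not support this. The loss depends on Section 15 being followed over Section 7.4, and even then some drugs with incomplete start dates would be kept through imputation.

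A reader might also infer that the primary endpoints are at risk, because daily infant dosage is concentration times expressed volume and some drugs alter milk supply. This does not follow either:
- No endpoint is computed from the medication table.
- Expressed volume does not enter RID, which uses average milk concentration times 150 mL/day/kg (SAP 17.3).
- Milk collection ends on Day 7, so a drug first taken after that cannot affect the milk results.
- Drugs that raise or lower milk production are prohibited during the study. Their use would be a deviation, listed under SAP Section 10 and summarised there if judged important. SAP Section 6.2 also allows affected data points to be excluded from the PK analyses.

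Finally, it is tempting to say that Section 7.4 excludes a drug that began earlier and stopped on Day 1. Its words, "that started before or on Day 1 and continued through Day 1", can be read to include the last day, while the parenthesis after them points the other way. The case is unclear rather than excluded.

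These points limit the consequence. They do not remove the conflict, and the deviation listing does not cover permitted medications.

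**Conclusion.** The concern holds as an internal contradiction in the SAP with a limited effect. Section 15, as written, is a wrong rule for the table it specifies: a medication with a known start on or after the first dose has no class, whereas Section 7.4 classes it as concomitant.

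If Section 15 is followed, the descriptive medication tables omit all such medications, and the listing may do so too, since it is described as one of prior and concomitant medications. The records remain in the eCRF. No estimate of daily infant dosage, RID or any secondary PK endpoint changes.

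The conclusion assumes that dates are complete and that Section 15 is programmed literally. It should be corrected before the tables are programmed, but it gives no reason to doubt the PK results.

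**What to change.** Delete the two definitions in SAP Section 15, refer to Section 7.4 instead, and reword Section 7.4 so that one rule applies throughout:
- **Prior:** stopped before the date of first dose.
- **Concomitant:** any medication taken on or after the date of first dose through FU1, whatever its start date.

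With complete dates, every medication taken up to FU1 then falls into exactly one class. A drug that ends on Day 1 is concomitant, which settles the case that Section 7.4 leaves unclear. A recorded exact start date no longer causes a drug to be dropped. The window also matches the period over which concomitant medications are reviewed.

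The cost is SAP wording only: no new data, visits or protocol change.
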